7.3.4 Physical Measurements

Physical measurements such as body weight, height, waist circumference and body mass index (BMI) will be listed for all treated subjects. Measurements will also be summarized by nominal visit for all treated subjects, as overall and by treatment.

7.3.5 Medical History and Previous Medications

Medical history and previous medications taken prior to dosing will be listed for all treated subjects.

7.4 Extent of Exposure

Extent of exposure for 16-week double blinded treatment period will be summarized for all treated subjects, presenting the numbers and percentage of subjects with an extent of exposure within the following day ranges by treatment group: 1 to 15, 16 to 29, 30 to 43, 44 to 57, 58 to 86, 87 to 112 and > 112. Also the mean, SD, median and range of the extent of exposure to blinded treatment will be presented by treatment group. Study drug administration, randomization schedule will be documented as per subject listings. Any non-study medications taken by subjects, any conducted non-study medical treatment procedures, and any utilized non-study diagnostic procedures will also be listed.

7.5 Efficacy

To evaluate the effect of BMS-986036 on change in hepatic fat fraction (%) by MRI in subjects with biopsy-proven NASH after 16 weeks of treatment, a longitudinal repeated measures analysis will be used to analyze the change in hepatic fat fraction (%) from baseline to Week 16 in the treated population who have both a baseline and at least one post-baseline measurement. The model will include treatment group, week and treatment-by-week interactions as main effects and baseline hepatic fat fraction (%) and baseline diabetic status as covariates. An unstructured covariance matrix will be used to represent the correlation of the repeated measures within each subject. The model will provide point estimates, standard errors and 2-sided 90% confidence intervals for mean change from baseline at all time points within and between treatments. P-values will be calculated to compare the treatment effect in each of two BMS-986036 (10 mg daily and 20 mg weekly) treatment groups to that in the placebo treatment group at Week 16. Each treatment group comparison will be performed at a one-sided 0.05 significance level. No adjustment will be made for multiplicity.

Summary statistics will be tabulated for all treated subjects by treatment, study day for hepatic fat fraction (%) with corresponding change from baseline. Plot of mean profile over time will also be provided for hepatic fat fraction (%) by treatment. In addition, the descriptive statistics for hepatic fat fraction (%) will be summarized by baseline NASH CRN fibrosis staging (1, 2, 3), type 2 diabetes mellitus (yes, no), NAS (NAFLD activity score) and fatty liver index.

Two sensitivity analyses will be performed in the longitudinal repeated measure analysis.

- For patients without measurement at week 16 for hepatic fat fraction (%), last observation for hepatic fat fraction (%) measured on or after Day 86 will be carried forward to be the value at week 16.
- Baseline NASH CRN fibrosis staging and the treatment-by-baseline diabetic status interactions will be included in the model. The effect of BMS-986036 on the change in hepatic fat fraction (%) from baseline to week 16 within each stratum will be analyzed.

7.6 Safety

Analysis of all safety data will follow the BMS guideline of analysis of safety data.¹⁰

The evaluation of safety is based on clinical adverse events (AEs), vital signs, ECGs results, physical examinations, clinical laboratory results, the result of DXA scan for bone mineral density as well as injection assessment reported during the study.

All recorded adverse events will be listed and tabulated by system organ class, preferred term, treatment and overall. Any physical examination findings will be listed. ECG, vital signs and clinical laboratory test results and corresponding change from baseline will be listed and summarized by treatment group. Values for ECG, vital signs and clinical laboratory test results outside the pre-specified criteria will also be listed and summarized. ECG readings will be evaluated by the Investigator and abnormalities, if present, will be listed. Bone mineral density (BMD) results will be tabulated.

Where appropriate, baseline is defined as the last non-missing result with a collection date-time less than the date-time of the first active dose of study medication, for laboratory results, vital signs, ECG and BMD results.

7.6.1 Deaths

All reported deaths after a subject is enrolled (i.e., has signed the informed consent) will be listed separately by subject for all enrolled subjects.

7.6.2 Serious Adverse Events

All reported serious adverse events (SAEs) will be listed for all enrolled subjects and may also be summarized for all treated subjects by treatment as needed.

7.6.3 Adverse Events

All AEs will be coded and grouped into Preferred Terms (PT) by System Organ Class (SOC), using current version of Medical Dictionary for Regulatory Activities (MedDRA). All AEs will be summarized and listed by SOCs and PTs.

Adverse events which occur during the lead-in period will be tabulated for all lead-in subjects as overall. And adverse events which occur on or after the first active dose of study treatment will be tabulated for all treated subjects by treatment. Events will be assigned to the study treatment administered to the subject. The proportion of subject having an adverse event will be calculated

as the number of subjects experiencing the event, divided by the total number of subjects receiving study treatment.

All AE listings will indicate the unique subject identifier, age, gender, current treatment, the date of onset, the date of resolution, day of onset relative to the start of treatment, action taken, investigator's assessment of severity and relationship to study drug. Additional listings will be provided for adverse events leading to discontinuation and adverse events without recorded resolution. Summaries of adverse events will include adverse events, adverse events by intensity and adverse events by relationship. Adverse events leading to discontinuation may also be summarized as needed.

Where a subject has the same adverse event, based on preferred terminology, reported multiple times in a single analysis period, the subject will only be counted once at the preferred terminology level in adverse event frequency tables.

Where a subject has multiple adverse events within the same system organ class in a single analysis period, the subject will only be counted once at the system organ class level in adverse event frequency tables.

When a subject has the same adverse event, based on preferred terminology, reported multiple times in a single analysis period, the following criteria, in order of precedence, will be used to select the event to be included in summary tables:

- Relationship to study medication
- Intensity of event
- Onset date and time

When reporting adverse events by intensity, in addition to providing a summary table based on the event selection criteria detailed above, summary tables will also be provided based on the most intense event during the analysis period - independent of relationship to study medication. For these tables, the following criteria, in order of precedence, will be used to select the event to be included in summary tables:

- Intensity of event
- Onset date and time

Subjects will only be counted once in the 'Total' at their maximum intensity, regardless of SOC or PT.

In addition, a summary of exposure adjust AEs including multiple occurrences of unique events will be reported if there are at least 5% of treated subjects with multiple occurrences of unique events in any treatment group during double-blinded period. A by-subject listing of unique events will be provided.

Injection site reactions as a target physical examination will be monitored from Day -7 through the end of the out-patient follow-up period. The Draize Scale for erythema and edema will be used

as a guide for reporting AEs at the blinded study drug injection site, see Table 5.3.3-1 in the protocol. In addition, for injection site reaction will be summarized as a separate frequency table and listed.

7.6.4 Clinical Laboratory Evaluations

The results of all protocol-specified clinical laboratory tests, as well as laboratory results outside of the normal range, will be listed for all treated subjects. Scheduled laboratory measurements and corresponding change from baseline values will be summarized by treatment and nominal visit for each laboratory test. Laboratory abnormalities are determined from laboratory measurements analyzed at the central or local laboratory, and are graded using the Division of AIDS (DAIDS) Table for Grading the Severity of Adult and Pediatric Adverse Events.¹¹

For each laboratory test, emergent laboratory abnormalities (not emergent, grade 1, grade 2, grade 3, grade 4, grade 1 to 4; grade 3 to 4) are summarized by treatment for all treated subjects. On-treatment emergent abnormalities are those with a higher toxicity grade than the baseline toxicity grade (including missing baseline). Laboratory abnormalities regardless of baseline toxicity grade are also summarized analogously by treatment. Commonly collected laboratory tests with DAIDS toxicity grades may include the following: hemoglobin, leukocytes, lymphocytes (absolute), neutrophils + bands (absolute), platelet, ALT, AST, total bilirubin, Direct bilirubin, alkaline phosphatase, GGT, albumin, INR, creatinine, calcium, phosphorus, magnesium, fasting glucose.

Laboratory abnormalities on treatment are also summarized by baseline toxicity grade (grade 0; grade 1, grade 2; grade 3, grade 4) and treatment regimen for the following laboratory tests: ALT, AST, total bilirubin, direct bilirubin, alkaline phosphatase, calcium.

The laboratory value during the study period with the highest toxicity grade is reported for each test.

Laboratory results for subjects with any laboratory abnormality with grade 3 and grade 4 (scheduled and unscheduled) will be listed.

7.6.5 ECG

All recorded electrocardiograms will be listed.

If Fridericia's corrected QT (QTcF) is not available in the database, QTcF will be calculated using the reported uncorrected QT Interval and Heart Rate, and the following formula:

$$QTcF = \frac{QT}{(60/HEARTRATE)^{1/3}}$$

If Bazett's corrected QT (QTcB) is not available in the database, QTcB will not be calculated.

Summaries of ECG parameters (heart rate (HR), QT (QT, Bazett's corrected QT [QTcB], Fridericia's corrected QT [QTcF]), PR and QRS intervals) will be tabulated for all treated subjects by study day and treatment. Summaries of ECG parameters will include change from baseline at list of time points.

Subjects with ECG intervals outside of a pre-specified range will also be listed.

The following criteria (Table 7.6.5-1) will be used to determine ECG results that are outside of a pre-specified range:

Table 7.6.5-1: Criteria for ECG Results Outside of a Pre-specified Range

PR (msec):	Value > 200
QRS (msec):	Value > 120
QT (msec):	Value > 500 or change from baseline > 30
QTcB (msec):	Value > 450 or change from baseline > 30
QTcF (msec):	Value > 450 or change from baseline > 30

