- q. Inability to be venipunctured and/or tolerate venous access.
- r. Inability to comply with all protocol assessments including the follow-up visits.
- s. Any other sound medical, psychiatric and/or social reason as determined by the investigator.

2. Physical and Laboratory Test Findings

- a. Evidence of organ dysfunction or any clinically significant deviation from normal in physical examination, vital signs, ECG or clinical laboratory determinations beyond what is consistent with the target population.
- b. ALT level $\geq 5 \times \text{ULN}$
- c. Albumin <3.5 g/dL (35 g/L)
- d. INR (International Normalized Ratio) >1.3
- e. Total bilirubin ≥ 1.5 mg/dL (≥ 25.6 $\mu\text{mol/L}$)
- f. Platelet count <100 x 10⁹/L
- g. Alpha fetoprotein (AFP):

- AFP > 100 ng/mL (> 82.6 IU/mL), OR
 - AFP ≥ 50 and ≤ 100 ng/mL (≥ 41.3 IU/mL and ≤ 82.6 IU/mL) requires a liver ultrasound. Subjects with findings suspicious for HCC are excluded.
- h. HbA1c $\geq 9.5\%$
 - i. Positive blood screen for hepatitis C antibody, hepatitis B surface antigen (via Screening lab).
 - j. Subjects with a centrally read Screening DXA T-score at the total spine, total hip or femoral neck, less than or equal to -2.5 S.D. (a worse score would be -3.0 S.D., for example).
 - k. Uncontrolled hypertension (systolic blood pressure [SBP] ≥ 160 , and/or diastolic blood pressure [DBP] ≥ 95 mmHg). Anti-hypertensive medications are permitted if the dose has been stable for >2 weeks before Screening.
 - l. QTcF > 480 msec on 12-lead electrocardiogram (ECG) during the Screening period, confirmed by repeat.
 - m. Impaired renal function defined as an estimated glomerular filtration rate (GFR) of <49 mL/min/1.73m² using Modification of Diet in Renal Disease (MDRD) equation. A repeat measurement of screening serum creatinine is permitted when the investigator suspects that initial screening results may have been affected by volume contraction (e.g., prolonged fasting, diuretic use) or other transient conditions. Note: $GFR (mL/min/1.73 m^2) = 175 \times (\text{Serum creatinine})^{-1.154} \times (\text{Age})^{-0.203} \times (0.742 \text{ if female}) \times (1.212 \text{ if African American})$.

3. Allergies and Adverse Drug Reaction

- a. History of allergy to PEGylated compounds or FGF21-related compounds.
- b. History of hypersensitivity to protein-based therapeutics.
- c. History of any significant drug allergy (such as anaphylaxis or hepatotoxicity).

4. Other Exclusion Criteria

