7.6.6 Vital Signs

Vital signs parameters (systolic blood pressure, diastolic blood pressure, heart rate, respiratory rate and body temperature) will be listed. Summaries of vital sign parameters will be provided for each vital sign parameter at corresponding visits for all treated subjects by treatment and respective changes from baseline.

Subjects with vital signs outside of a pre-specified range will also be listed.

The following criteria will be used to determine vital sign results that are outside of a pre-specified range, where changes from baseline are based on matched postural positions and are calculated as parameter value - baseline parameter value:

Table 7.6.6-1: Criteria for Vital Signs Results Outside of a Pre-specified Range

Heart Rate(bpm)	Value > 100 and change from baseline > 30, or Value < 55 and change from baseline < -15
Systolic BP(mmHg)	Value > 140 and change from baseline > 20, or Value < 90 and change from baseline < -20
Diastolic BP(mmHg)	Value > 90 and change from baseline > 10, or Value < 55 and change from baseline < -10
Respiration(breaths/min)	Value > 16 or change from baseline > 10
Temperature (°C)	Value > 38.3°C or change from baseline > 1.6°C

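### The ECG, respiration and temperature flags do not separate values already beyond the limit at baseline from new ones; add baseline-split counts beside them

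*SAP*

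**What the plan says.** **ECG rules (SAP 7.6.5, Table 7.6.5-1).** QTcF and QTcB are flagged on "Value > 450 or change from baseline > 30" and QT on "Value > 500 or change from baseline > 30". PR above 200 msec and QRS above 120 msec are flagged with no baseline term.

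**Vital-sign rules (SAP 7.6.6, Table 7.6.6-1).** Respiration is flagged on "Value > 16 or change from baseline > 10" and temperature on "Value > 38.3°C or change from baseline > 1.6°C". Heart rate needs both parts, for example "Value > 100 and change from baseline > 30", and both blood pressures have that same form.

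**Eligibility (Protocol 3.3.2, exclusion 2.l).** The QTcF exclusion is "QTcF > 480 msec on 12-lead electrocardiogram (ECG) during the Screening period, confirmed by repeat". A subject can therefore enter at 451 to 480 msec.

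**Use of the flags.** SAP 7.6.5 says only "Subjects with ECG intervals outside of a pre-specified range will also be listed". SAP 7.6 goes further: "Values for ECG, vital signs and clinical laboratory test results outside the pre-specified criteria will also be listed and summarized".

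**Laboratory tests (SAP 7.6.4).** Two counts are planned: emergent abnormalities, whose grade must exceed the baseline grade, and abnormalities whatever the baseline grade was.

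**Endpoint (SAP 4.2, Protocol 8.3.1).** Marked abnormalities in ECGs and vital signs are among the primary safety endpoints. The visible text gives no definition of them other than these two tables.

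**The concern.** For PR, QRS, QT, QTcB, QTcF, respiration and temperature, a value beyond the limit is flagged whether or not it was already there before the first active dose. For QTcF this can happen by design, because the flag lies 30 msec below the entry limit (480 − 450 = 30). A summary count then puts three kinds of subject into one cell: those who came in above the limit and did not change, those who crossed it after dosing, and those with a large rise that stayed below it.

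The SAP already separates such cases elsewhere. Heart rate and blood pressure need a limit and a change, and laboratory tests get an emergent count beside the overall one. No reason is given for treating the ECG intervals, respiration and temperature differently. With about 30 subjects per arm (Protocol 3.1), a few carried-in values can blur or imitate a difference between arms.

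**Working it through.** The plan states no expected number of flags, so there is no figure to reproduce. The check applies the rules as written and then illustrates the size under stated assumptions.

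**1. QTcF rule applied to baseline → post-baseline pairs (msec)**

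| Pair | Change | Written rule (> 450 or change > 30) | Newly > 450 | Already > 450 | Change > 30 |
|---|---|---|---|---|---|
| 470 → 470 | 0 | flagged | no | yes, not worse | no |
| 475 → 455 | −20 | flagged | no | yes, not worse | no |
| 455 → 484 | +29 | flagged | no | yes, worse | no |
| 445 → 470 | +25 | flagged | yes | no | no |
| 400 → 431 | +31 | flagged | no | no | yes |
| 430 → 465 | +35 | flagged | yes | no | yes |

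All six fall in one category under the written rule. The last three columns separate them and drop none.

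**2. Respiration (breaths/min).** The written rule flags 18 → 18 and 20 → 17, neither of which is a worsening. Requiring both parts would remove those two, but it would also remove 14 → 22 (+8) and 16 → 26 (+10), because neither change exceeds 10. Both are new values above 16.

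**3. Share of subjects entering above the QTcF flag (assumption: normal, SD 20 msec).** P(450 to 480) = Φ((480 − mean)/20) − Φ((450 − mean)/20).

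- Mean 410: Φ(3.5) − Φ(2.0) = 2.3%, × 30 = 0.7 per arm
- Mean 420: Φ(3.0) − Φ(1.5) = 6.5%, × 30 = 2.0 per arm
- Mean 430: Φ(2.5) − Φ(1.0) = 15.2%, × 30 = 4.6 per arm

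**4. Flags at one post-baseline ECG with no drug effect (simulation).** Assumptions: mean 410 to 430, between-subject SD 15 to 20, within-subject SD 8 to 12, baseline at most 480.

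- Flagged by the written rule: 1.3% to 20.5% of subjects, or 0.4 to 6.1 per arm of 30.
- Share of those flags that are carried in (baseline > 450 and change ≤ 30): 8% to 66%.
- Carried-in flags per arm = 30 × flag rate × carried-in share. The lowest case is 30 × 0.013 × 0.25 = 0.1 (mean 410, SDs 15 and 8). The highest is 30 × 0.170 × 0.66 = 3.4 (mean 430, SDs 20 and 8).

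**5. Respiration over repeated visits (assumption: a share q of readings exceeds 16).** Vital signs are scheduled on Days 15, 29, 43, 57, 86, 112 and 142. Fully stable readings flag 30 × q subjects per arm at least once; independent readings flag 30 × (1 − (1 − q)^7).

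- q = 10%: 3.0 (stable) to 15.7 (independent)
- q = 50%: 15.0 (stable) to 29.8 (independent)

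Day 142 falls after the SAP 6.1 On-Treatment period, which ends 14 days after the last dose. With the six earlier visits the independent figures are 30 × (1 − 0.9^6) = 14.1 and 30 × (1 − 0.5^6) = 29.5.

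**The case against.** Much of the opposing case stands and limits the point.

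- **The rules do not ignore baseline altogether.** QT, QTcB, QTcF, respiration and temperature each have a change term; only PR and QRS have none. The difficulty is that the limit alone is enough.
- **The flags are not labelled emergent or on-treatment.** A reader might infer that the SAP counts carried-in values as drug effects. It describes only a range screen, and it does not expressly tie the marked-abnormality endpoint to these tables.
- **The laboratory contrast is partial.** Laboratory abnormalities are also counted without regard to baseline, so absolute counts are a deliberate choice. What ECG and vital signs lack is the second, baseline-adjusted count.
- **450 and 480 are not contradictory.** A review flag and an entry limit may differ. Exclusions 1.n and 2.a also screen out significant cardiac illness and clinically significant ECG deviations, which may reduce the number entering high.
- **Repeat counting of ECGs is limited.** After Day 1 the scheduled ECGs are Day 112 (or early termination) and Day 142, the latter in follow-up.
- **A respiratory rate above 16 cannot be called ordinary from these documents.** Nor can a near-universal flag be inferred, since no distribution is given. The argument rests on the mismatch with heart rate and blood pressure.
- **Other outputs help.** All ECGs are listed, changes from baseline are summarized, investigators evaluate the ECGs, and no test on the flags is planned. The Data Presentation Plan and the sponsor's safety guideline, which are not available here, may add detail.

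These points make the matter small but do not remove it. Mean changes and listings do not give a count of subjects newly beyond a limit, and SAP 7.6 promises a summary of the flagged values.

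**Conclusion.** The point holds as a minor improvement to the safety tables. As written, the counts for the five ECG intervals, respiration and temperature mix values present before dosing with new or worsened ones. Because treatment is randomized, carried-in values are expected equally in all arms: they add noise to a comparison of about 30 per arm, not directional bias. Efficacy, type I error and sample size are untouched.

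The rule logic follows from the documents alone. The size does not: the 0.1 to 3.4 carried-in QTcF flags per arm, and all the respiration figures, depend on assumed distributions and serve only as illustration. Temperature is included because its rule has the same form; nothing in the documents sizes the effect there.

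**What to change.** Keep the absolute flags in Tables 7.6.5-1 and 7.6.6-1. For PR, QRS, QT, QTcB, QTcF, respiration and temperature, add beside them, by treatment:

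- (a) newly out of range: post-baseline value beyond the limit, baseline not beyond it;
- (b) already out of range at baseline, split by whether the post-baseline value is worse than baseline;
- (c) change from baseline beyond the SAP's existing threshold, as its own row, where there is one (PR and QRS have none).

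Use the baseline already defined in SAP 7.6. The split in (b) keeps a case such as QTcF 455 → 484 visible, which (a) and (c) would both miss. Do not change respiration from *or* to *and*: new values such as 14 → 22 and 16 → 26 would no longer be flagged.

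The cost is SAP table wording, a few more table rows and minor programming. No new data are needed, and no value flagged now is lost.

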7.6.6 Vital Signs

Vital signs parameters (systolic blood pressure, diastolic blood pressure, heart rate, respiratory rate and body temperature) will be listed. Summaries of vital sign parameters will be provided for each vital sign parameter at corresponding visits for all treated subjects by treatment and respective changes from baseline.

Subjects with vital signs outside of a pre-specified range will also be listed.

The following criteria will be used to determine vital sign results that are outside of a pre-specified range, where changes from baseline are based on matched postural positions and are calculated as parameter value - baseline parameter value:

Table 7.6.6-1: Criteria for Vital Signs Results Outside of a Pre-specified Range

Heart Rate(bpm)	Value > 100 and change from baseline > 30, or Value < 55 and change from baseline < -15
Systolic BP(mmHg)	Value > 140 and change from baseline > 20, or Value < 90 and change from baseline < -20
Diastolic BP(mmHg)	Value > 90 and change from baseline > 10, or Value < 55 and change from baseline < -10
Respiration(breaths/min)	Value > 16 or change from baseline > 10
Temperature (°C)	Value > 38.3°C or change from baseline > 1.6°C

